12.1 Disposition of Subjects and Discontinuations

A table on screened subjects describing the number and percent of subjects in each of following disposition categories will be produced by treatment group:

Table 5: Disposition

	Primary analysis	Final analysis
Total number of screened subjects, ie subjects that gave informed consent (overall summary only)	✓	✓
Number of subjects who discontinued prior to randomization and reason (overall summary only)	✓	✓
Number of randomized subjects	✓	✓
Number of randomized subjects who did not start treatment	✓	✓
Number of randomized subjects who completed 12-week double-blind treatment period	✓	✓
Number of randomized subjects who permanently discontinued treatment during 12-week double-blind treatment period and reason	✓	✓
Number of randomized subjects who discontinued from trial after randomization during 12-week double-blind treatment period and reason	✓	✓
Number of randomized subjects who declined to participate in OLE and discontinued from trial after completion of 12-week double-blind treatment period during safety follow-up and reason	✓	✓
Number of randomized subjects who declined to participate in OLE and completed safety follow-up period according to protocol	✓	✓
Number of randomized subjects who agreed to participate in OLE period	✓	✓
Number of randomized subjects with a gap > 4 weeks between double-blind period and OLE period		✓
Number of randomized subjects who completed the OLE period		✓
Number of randomized subjects who permanently discontinued treatment during OLE period and reason		✓
Number of randomized subjects who discontinued from trial after randomization during OLE period and reason		✓
Number of randomized subjects who completed safety follow-up after OLE according to protocol		✓
Number of randomized subjects who discontinued from trial after completion of OLE period during safety follow-up and reason		✓

For the primary analysis, a table of randomized subjects not treated as randomized, including reason for not being treated as randomized will be produced by randomized treatment group.

A table based on screened subjects, describing the number and percent of subjects in each analysis set by treatment group, will be produced:

Table 6: Analysis sets

	Primary analysis	Final analysis
Number of screened subjects	✓	✓
Number of randomized subjects	✓	✓
Number of subjects included in the SAF	✓	✓
Number of subjects included in the OLE SAF		✓
Number of subjects included in the PK Analysis Set	✓	✓
Number of subjects included in the PD Analysis Set	✓	✓
Number of subjects included in the OLE PD Analysis Set		✓
Number of subjects included in the CCI	✓	✓
Number of subjects included in the mITT Analysis Set	✓	✓
Number of subjects included in the OLE mITT Analysis Set		✓

A table based on screened subjects, describing the number and percent of subjects in each region (eg Europe, European Economic Area (as required by EudraCT) and North America), country within region and site, by analysis set, will be produced.

A table based on randomized subjects with patients still on trial at each visit will be also produced. This table will also include the number of patients who discontinued before each visit.

Corresponding individual listings will be prepared. Discontinued subjects (from treatment or study) will be listed with their reason for withdrawal (from treatment or study). Additionally, a listing of the subjects screened but not randomized will be produced with the reason for not being randomized. A listing of randomized subjects with subject number, randomization date, and randomized treatment group, ordered by randomization number within randomization stratum, will be produced for the purpose of assessing whether randomization was conducted as planned.

The list of re-screened subjects and corresponding subject identifiers will be provided. These subjects' identifiers will be listed. Only the second subject identifier will be used in statistical descriptions and analyses, while the first identifier will not be considered/excluded from the disposition counts.

12.2 Protocol Deviations

The Table 7 summarizes how protocol deviations will be handled for both primary and final analysis:

Table 7: Protocol deviations

Analysis	Period covered for protocol deviations reporting	Treatment Group	Observation Period	Analysis Set
Primary analysis	12-Week treatment period	Placebo or M2951 50 mg BID	First dose of 12-Week treatment period up to first dose of OLE, or last observed dose during the 12-Week treatment period if subject either prematurely discontinues from treatment or declines to participate in OLE	Randomized
Final analysis	OLE	Placebo/M2951 50 mg BID	First dose of OLE to last observed dose	Randomized and entered into OLE
	12-Week treatment period + OLE	M2951 50 mg BID/M2951 50 mg BID	First dose to last observed dose	Randomized and entered into OLE

12.2.1 Important Protocol Deviations

The following summary tables and listings of important protocol deviations will be provided (separately for pre-/post inclusion deviations):

- Table providing frequency for each type of important protocol deviation
- Listing of important protocol deviations

12.2.2 Clinically Important Protocol Deviations

Clinically important protocol deviations, as defined in Section 10.1 and Section 10.2, will be summarized and listed.

Deviations, or changes to the procedures or events that may have a relevant influence on the PK/PD analysis or impact the quality of the PK/PD data may lead to exclusion from the PK/PD analysis sets. Examples include, but may not be limited to, the following:

- Adverse events, vomiting, diarrhea etc.
- Vomiting following oral dosing (these instances will be discussed on a case-by-case basis)
- Sample processing errors that may lead to inaccurate bioanalytical results
- Inaccurate dosing or dosing errors
- Concomitant medication violations (see Section 6.5.2. of the protocol)

In the case of a deviation or event that may affect PK, PK data collected during the affected study day will be excluded from the study results after consultation and agreement with Sponsor or sponsor representative. Other changes to the procedures or events which do not impact the quality of the PK data will not be considered clinically important protocol deviations. A common example of a protocol deviation that is not clinically important is a missed PK blood sample or deviations from PK blood collection times, with the requirement that the actual time of collection is recorded. An exception to a PK blood sample deviation defined as not clinically important is the predose sample which will be considered a deviation if it is not collected predose, and the 6 hour sample if missing or collected 10 minutes outside the scheduled window.

If subjects or select M2951 concentrations are excluded from the PK analysis set, the excluded PK data will be listed in the CSR and flagged.

13 Demographics and Other Baseline Characteristics

Demographics and baseline characteristics will only be summarized for the primary analysis.

Demographics and baseline characteristics will be summarized on SAF and presented by treatment group and overall. All data will be listed on SAF.

13.1 Demographics

- Demographic characteristics
 - Sex: male, female
 - Race: White, Black or African American, Asian, American Indian or Alaska Native, Native Hawaiian or Other Pacific Islander, Other
 - Ethnicity: Hispanic or Latino, Not Hispanic or Latino
 - Age (years) at informed consent: summary statistics
 - Age categories :
 - < 65 years, ≥ 65 years
- Geographic Region (eg Europe, North America)
- European Economic Area (Yes/No)

Specifications for computation:

- Age (years):

- $(\text{date of given informed consent} - \text{date of birth} + 1) / 365.25$
- In case of missing day for at least one date, but month and year available for both dates:
For the derivation of age, the day of informed consent and the day of birth will be set to 1 and the formula above will be used
- In case of missing month for at least one date, but year available for both dates:
For the derivation of age, the day and the month of informed consent and the day and month of birth will be set to 1 and the formula above will be used
- Site codes will be used for the determination of the subject's geographic region and European Economic Area membership.

13.2 Medical History

The medical history will only be summarized for the primary analysis.

The medical history will be summarized using Medical Dictionary for Regulatory Activities (MedDRA), current version, PT as event category and MedDRA SOC body term as Body System category. The MedDRA version used will be indicated in footnote. Medical history will be tabulated by SOC and PT. SOC and PT will be alphabetically sorted. Medical history will be also listed.

13.3 Other Baseline Characteristics

13.3.1 Disease history

Information on RA baseline disease characteristics collected during screening will only be summarized for the primary analysis.

Information on RA baseline disease characteristics collected during screening will be summarized in total and by treatment arm. Descriptive statistics will be presented for:

- Time (months) since confirmed diagnosis of RA according to 2010 ACR/The EULAR RA classification criteria. Time will be computed as $(\text{Date of Informed Consent Signature} - \text{Date of confirmed diagnosis of RA}) / 30.4375$. If the date of confirmed diagnosis of RA is entirely missing, then time since confirmed diagnosis of RA will not be computed. In case of partial missing date of confirmed diagnosis of RA, this date will be imputed as follows:
 - If only the day is missing, then it will be replaced by the first day of the month
 - If both day and month are missing, then it will be replaced by the first of January
- The count of Tender Joint Count 68 (TJC68)
- The count of Swollen Joint Count 66 (SJC66)

- Physician's Global Assessment of Disease Activity using horizontal Visual Analog Scale (VAS) in mm
- Subject's Global Assessment of Disease Activity using horizontal VAS in mm
- Subject's Assessment of Pain using horizontal VAS in mm
- Subject's Assessment of Physical Function as measured by HAQ-DI will be derived ([Appendix 1: HAQ-DI scoring](#)) and described overall and by dimensions (dressing and grooming, getting up, eating, walking, hygiene, reach, grip, activities)
- hsCRP (mg/L) as a continuous variable and by category (normal/high based on central normal laboratory ranges)
- ESR (mm/Hr) as a continuous variable and by category (low/normal/high based on local normal ranges collected in eCRF)
- Acute-phase reactant (at least one test result is needed for the classification): normal hsCRP and normal ESR, abnormal hsCRP or abnormal ESR. Abnormal refers to either low or high normal range classification.
- RF (expressed in kU/L) as a continuous variable and classified as negative (\leq Upper Limit of Normal [ULN]) and positive ($>$ ULN)
- Anti-CCP antibodies classified as a continuous variable and as negative (\leq ULN) and positive ($>$ ULN)
- Serology (at least one test result is needed for the classification): negative RF and negative anti-CCP (\leq ULN), low-positive RF or low-positive anti-CCP ($>$ ULN, $\leq 3*ULN$), high-positive RF or high positive anti-CCP ($>$ $3*ULN$)
- DAS28-hsCRP, derived using formula presented in [Appendix 2](#), summarized as a continuous variable and by disease activity category ($<$ 2.6 [remission], ≥ 2.6 to ≤ 3.2 [low], $>$ 3.2 to ≤ 5.1 [moderate] and $>$ 5.1 [high]).

13.3.2 Other

Physical examination will only be summarized for the primary analysis.

Descriptive statistics will be presented for physical examination as continuous variables: height (cm), weight (kg) and BMI (kg/m²).

14 Previous or Concomitant Medications/Procedures

Medications/procedures will be presented according to Table 8:

Table 8: Data handling for medications/procedures

Analysis	Period covered	Treatment groups	Data summarized	Analysis sets
Primary analysis	12-Week treatment period	Placebo or M2951 50 mg BID	Previous medications + concomitant medications	SAF
Final analysis	OLE	Placebo/M2951 50 mg BID	Concomitant medications only	OLE SAF
	12-Week treatment period + OLE	M2951 50 mg BID/M2951 50 mg BID	Concomitant medications only	OLE SAF

The definition of previous or concomitant medication is presented in Table 9:

Table 9: Definition of previous/concomitant medication

Analysis	Period covered	Treatment groups	Definition
Primary analysis	12-Week treatment period	Placebo or M2951 50 mg BID	
Previous medications are medications, other than trial medications, which either:
 
 started and stopped before first administration of any IMP (Placebo or M2951). started prior to the first administration of IMP (Placebo or M2951) and are taken by subjects on or after the first administration of IMP.
			
Concomitant medications are medications, other than IMPs, which either:
 
 started on or after the first administration of any IMP (Placebo or M2951). started prior to the first administration of IMP (Placebo or M2951) and are taken by subjects on or after the first administration of IMP.
Final analysis	OLE	Placebo/M2951 50 mg BID	
Concomitant medications are medications, other than IMPs, which either:
 
 started on or after the first administration of M2951 during OLE. started prior the first administration of M2951 during OLE and are taken by subjects on or after the first administration of M2951 during OLE.
	12-Week treatment period + OLE	M2951 50 mg BID/M2951 50 mg BID	
Concomitant medications are medications, other than IMPs, which either:
 
 started on or after the first administration of M2951 during 12-Week treatment period. started prior the first administration of M2951 during 12-Week treatment period and are taken by subjects on or after the first administration of M2951 during 12-Week treatment period.

Partial dates will be handled as follows:

- For previous medications, in case the date values will not allow a medication to be unequivocally allocated to previous medication, the medication will be considered as previous medication.
- For concomitant medications, in case the date values will not allow a medication to be unequivocally allocated to concomitant medication, the medication will be considered as concomitant medication.

The ATC-2nd level and PT will be tabulated as given from the World Health Organization Drug Dictionary (WHO-DD) current version. In case multiple ATCs are assigned to a drug, all ATC-2nd level will be used for reporting.

The number and proportion of subjects with previous or concomitant medications (previous medications will not be summarized for final analysis) will be separately summarized by treatment group and will be presented by descending frequency of ATC 2nd level term and then by descending frequency of PT in total column. If multiple ATCs/PTs have the same frequency, they will be sorted alphabetically. The WHO-DD version used will be indicated in footnote.

Previous or concomitant medications will be also listed.

All concurrent procedures, which were undertaken any time on trial, will be summarized. Concurrent procedures will be classified by medical review. Number of subjects with concurrent procedures (prior, on or after the first day of IMP) overall and by type of procedure (as classified by medical review) will be summarized by treatment group.

Concurrent procedures will be also listed.

15 Treatment Compliance and Exposure

Exposure

Exposure will be separately analyzed for the 12-week treatment period, for the OLE period and overall (ie 12-Week treatment period + OLE).

Exposure for 12-week treatment period will only be presented for primary analysis, whereas exposure for OLE period and overall exposure will only be presented for final analysis.

The Table 10 summarizes how exposure time will be computed:

Table 10: Exposure time

Analysis	Period covered	Treatment groups	Exposure time	Analysis sets
Primary analysis	12-Week treatment period	Placebo or M2951 50 mg BID	From first dose of any IMP during 12-Week treatment period to last observed dose of 12-Week treatment period	SAF
Final analysis	OLE	Placebo/M2951 50 mg BID	From first dose of M2951 to last dose of M2951 during OLE	OLE SAF
	12-Week treatment period + OLE	M2951 50 mg BID/M2951 50 mg BID	From the first dose of M2951 during 12-Week treatment period to the last dose of M2951 during OLE	OLE SAF

12-week treatment period

Exposure for the 12-week treatment period will be presented on SAF.

For the 12-week treatment period, subjects will receive 50 mg bid M2951 or placebo administered as 2 matching oral capsules twice daily for 84 days. Each treatment kit contains enough medication for administration for 1 week + 2 days (ie 36 capsules). On trial visit days, subjects will be given treatment kits containing the number of capsules needed up to next planned trial visit. Subjects will self-administer IMP in a blinded manner at a set time each day (± 2 hours) as two matching capsules bid (morning and evening) for 12 weeks:

- Subjects randomized to placebo arm will take four placebo capsules filled with mannitol
- Subjects randomized to M2951 arm will take four capsules filled with 25 mg of M2951.

On trial visit days, IMP will be administered during the trial visit after the scheduled trial visit procedures (other than post treatment PK/PD sampling) are completed. Exposure time in weeks will be calculated according to the following formula:

$$\text{exposure (weeks)} = (\text{date of last dose} - \text{date of first dose} + 1) / 7$$

First dose refers to the first administration of any IMP in 12-week treatment period.

Exposure time will be presented by summary statistics and according to the following categories:

- ≤ 1 week
- > 1 to 2 weeks
- > 2 to 4 weeks
- > 4 to 8 weeks
- > 8 weeks

The cumulative actual dose (mg) per subject for the 12-week treatment period will also be summarized for the active treatment group. The cumulative actual dose is defined as the sum of the total dose levels that the subject received between first and last treatment dose: number of ingested capsules * 25mg. The number of ingested capsules will be computed as the difference between the dispensed amount of capsules and the returned amount of capsules. Cumulative actual dose cannot be calculated for placebo treatment group.

Study drug administrations will also be listed by treatment group, and subject, with start/end dates of administration, and reason for dose change or no dose (if applicable).

OLE period

Exposure for the OLE period will only be presented on patients from OLE SAF who switch from Placebo to M2951 50 mg BID.

After completing the treatment period, subjects will be offered the opportunity to participate in an optional 6-month M2951 extension period on Week 12 (Visit 8). Subjects who received M2951 during the treatment period will continue with the same dose of M2951 (in tablet formulation). All subjects in the placebo group during the treatment period will discontinue placebo and start treatment with 50 mg bid M2951 tablets on Day 1 of OLE. On trial visit days, the IMP will be administered during the trial visit after the scheduled trial visit procedures are completed.

Subjects will take 2 matching oral tablets twice daily for 6 months. Subjects will self-administer the IMP at a set time each day (± 2 hours).

Exposure time in weeks will be calculated according to the following formula:

$$\text{exposure (weeks)} = (\text{date of last dose} - \text{date of first dose} + 1) / 7$$

First dose refers to the first administration of M2951 in OLE period.

Exposure time will be presented by summary statistics and according to the following categories:

- ≤ 4 weeks
- > 4 to 8 weeks
- > 8 to 12 weeks
- > 12 to 16 weeks
- > 16 weeks

The cumulative actual dose (mg) per subject for the OLE period will also be summarized for both treatment groups. It is defined as for the 12-week treatment period.

Overall

Overall exposure will be presented on OLE SAF only for subjects who received M2951 during the 12-week treatment period and continue with the same dose of M2951 during OLE period.

Exposure time in weeks will be calculated according to the following formula:

$$\text{exposure (weeks)} = (\text{date of last dose} - \text{date of first dose} + 1) / 7$$

First dose refers to the first administration of M2951 in the study.

Exposure time will be presented by summary statistics and according to the following categories:

- ≤ 6 weeks
- > 6 to 12 weeks
- > 12 to 18 weeks
- > 18 to 24 weeks
- > 24 weeks

The cumulative actual dose (mg) per subject will be computed as well. It is defined as for the 12-week treatment period or OLE period.

Study drug administrations will also be listed by treatment group, and subject, with start/end dates of administration and reason for dose change (if applicable).

Compliance

Compliance will be separately analyzed for the 12-week treatment period, the OLE period and overall, in the same manner as exposure was analyzed (see Table 10).

For each analysis, a listing of kit number with date of dispense, number of ingested and returned capsules/tablets will also be provided.

12-week treatment period

Compliance for the 12-week treatment period will be presented on SAF.

For the 12-week treatment period, compliance with treatment is defined as the number of capsules taken during a period divided by the number of capsules that should have been taken during that period, multiplied by 100 to yield a percentage, ie:

compliance for X weeks of treatment =

$$100 * \left(\frac{((36 * X) - \text{number of returned capsules for } X_wk \text{ period})}{4 * \text{number of days between first intake and last intake of } X_wk \text{ period}} \right)$$

Compliance with treatment and the number of ingested capsules will be tabulated overall (ie from first intake to last intake of 12-week treatment period).

OLE period

Compliance for the OLE period will be presented on OLE SAF.

For the OLE period, compliance with treatment is defined using the same formula as for the 12-week treatment period, replacing capsules with tablets.

Compliance with treatment and the number of ingested tablets will be tabulated overall (ie from first intake to last intake during OLE period).

Overall

Overall compliance will be presented on OLE SAF only for subjects who received M2951 during the 12-week treatment period and continue with the same dose of M2951 during OLE period.

Overall compliance with treatment is defined using the same formula as for the 12-week treatment period, replacing capsules with capsules/tablets.

Compliance with treatment and the number of ingested capsules/tablets will be tabulated overall (ie from first intake to last intake of the study).

16 Endpoint Evaluation

For all efficacy endpoints, data selection for primary and final analyses will be handled as indicated in the Table 11:

Table 11 : Data handling for efficacy analysis

Analysis	Population	Period covered	Treatment groups	Data to be analyzed
Primary analysis	mITT Analysis Set	12-Week treatment period until start of OLE or discontinuation of treatment prior to OLE, whichever is applicable	Placebo or M2951 50 mg BID	All data collected during the 12-Week treatment period up to start of OLE if applicable
Final analysis	OLE mITT Analysis set	OLE period only	Placebo/M2951 50 mg BID only	Data from OLE period only, or posterior to OLE (Safety follow-up / End of Study)
		Both 12-Week treatment period and OLE period	M2951 50 mg BID/M2951 50 mg BID only	Data from both periods (12-Week treatment and OLE period), ie all data collected throughout the study

The Table 12 summarizes the analyses of efficacy endpoints:

Table 12 : Summary of efficacy endpoints for the primary analysis

Analysis	Endpoint	Method	Missing Data Handling
Primary endpoint	ACR20 at Week 12/Day 84	(1) Primary: Computation of response rate, point estimate and 2-sided 80% CI for Δ based on the “corrected Miettinen-Nurminen” method (2) Supportive**: logistic regression with treatment and baseline hsCRP as covariates	Primary: LOCF-NR (Table 3) Sensitivity: See Table 13
Key secondary endpoint	hsCRP CFB at Week 4/Day 28 and Week 12/Day 84	(1) Primary: ANCOVA model (2) Supportive: Hodges-Lehmann estimation for 80% CI	Primary: LOCF

Analysis	Endpoint	Method	Missing Data Handling
Other secondary endpoints	ACR20 response at each visit	(1) Primary: Computation of response rate, point estimate and 2-sided 80% CI for Δ based on the “corrected Miettinen-Nurminen” method (2) Supportive: logistic regression with treatment and baseline hsCRP as covariates	Primary: LOCF-NR (Table 3) Sensitivity: See Table 13
	ACR50/ACR70 response at each visit	(1) Primary: Computation of response rate, point estimate and 2-sided 80% CI for Δ based on the “corrected Miettinen-Nurminen” method (2) Supportive: logistic regression with treatment and baseline hsCRP as covariate	Primary: LOCF-NR (Table 3) Sensitivity: See Table 13
	CFB and percent CFB at each visit for each ACR component, ESR, anti-CCP, RF	Summary Statistics	As observed
	CFB in DAS28-hsCRP score at Week 4/Day 28, and Week 12/Day 84	(1) Primary : ANCOVA model (2) Supportive: Hodges-Lehmann estimation for 80% CI and ANCOVA model with baseline hsCRP as covariate	Primary: LOCF of each component prior to DAS28 calculation
	Percentage of subjects with DAS28-hsCRP < 3.2 (well-controlled disease) at Week 12/Day 84	(1) Primary: Computation of response rate, point estimate and 2-sided 80% CI for Δ based on the “corrected Miettinen-Nurminen” method (2) Supportive: logistic regression with treatment and baseline hsCRP as covariate	Primary: LOCF-NR (Table 3)
	Percentage of subjects with DAS28-hsCRP < 2.6 at Week 12 / Day 84	(1) Primary: Computation of response rate, point estimate and 2-sided 80% CI for Δ based on the “corrected Miettinen-Nurminen” method (2) Supportive: logistic regression with treatment and baseline hsCRP as covariate	Primary: LOCF-NR (Table 3)
** All supportive analysis will be based on the primary missing data imputation method. No sensitivity analysis of missing data imputation will be performed for all supportive analyses.			

The Table 13 summarizes the sensitivity analyses to be performed on missing data imputations:

Table 13 : Sensitivity analysis for the primary analysis

Endpoint	Method
ACR Response	
Non-responder imputation (NR): ACR20 response rate will be evaluated on mITT analysis set. Subjects with missing ACR score will be considered as non-responders.

	
Completely Missing at Random pattern (MCAR): ACR20 response rate will be evaluated as observed without any LOCF imputation on mITT analysis set.

	
Missing At Random pattern (MAR): ACR20 will be imputed using multiple imputations process using MI SAS procedure as follows:
 
 1. Monotone missing data structure will be created as follows: intermediate (non-monotone) missing data will be multiply imputed using the Markov chain Monte Carlo (MCMC) method and assuming MAR and multivariate normality. Transformation of data will only be used if there is a clear deviation from normality. The SAS procedure PROC MI with the MCMC option will be used with seed number=20170524. The number of burn-in iterations will be set to 200, which is the default value. Nevertheless, if diagnosis plots show that the convergence has not yet occurred, this will be adjusted. 2. Then, each component will be imputed with treatment group, hsCRP at baseline and data at previous visit from all ACR20 components as covariates. 3. Imputation will be repeated 1000 times. The ACR20 will then be calculated for each of the multiply imputed data sets from the imputed components. Results will be combined using MIANALYZE SAS procedure with the Rubin's rules.
	
Missing Not At Random pattern (MNAR): ACR20 will be imputed using multiple imputations process with MI SAS procedure for the MNAR pattern, using controlled-arm data with the MNAR statement from SAS MI procedure.

Subgroup analyses will be performed on the randomized subjects with either:

- hsCRP at screening ≥ 3.6 mg/L
- hsCRP at baseline ≥ 3.6 mg/L
- hsCRP at screening ≥ 5 mg/L
- hsCRP at baseline ≥ 5 mg/L

The Table 14 summarizes the analyses to be performed for each subgroup:

Table 14 : Subgroup analysis for the primary analysis

Endpoint	Method	Missing Data Handling
ACR20/ACR50/ACR70 response at each visit	Primary: Computation of response rate, point estimate and 2-sided 80% CI for Δ based on the “corrected Miettinen-Nurminen” method	Primary: LOCF-NR (Table 3)
CFB in hsCRP and DAS28-hsCRP score at Week 4/Day 28 and Week 12/Day 84	Primary : ANCOVA model Supportive: Hodges-Lehmann estimation for 80% CI, only if the assumption of normality is violated	Primary and supportive: LOCF of each component prior to DAS28 calculation
Percentage of subjects with DAS28-hsCRP < 3.2 (well-controlled disease) at Week 12/Day 84	Primary: Computation of response rate, point estimate and 2-sided 80% CI for Δ based on the “corrected Miettinen-Nurminen” method	Primary: LOCF-NR (Table 3)
Percentage of subjects with DAS28-hsCRP < 2.6 at Week 12 / Day 84	Primary: Computation of response rate, point estimate and 2-sided 80% CI for Δ based on the “corrected Miettinen-Nurminen” method	Primary: LOCF-NR (Table 3)

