PDEV35	Subjects receiving medications, herbal supplements, or food known to be moderate or strong inhibitors of CYP3A or drugs mainly metabolized by CYP3A (see Section 6.5.2 of CTP)	Yes	Yes	Eligibility and Entry Criteria	Exclusion criteria #24	If identified by medical review or corresponding exclusion criterion is ticked Yes.
PDEV36	Concurrent treatment with a non-permitted drug or procedure (refer to section 6.5.2 of CTP).	Yes	case by case basis			If identified by medical review.
PDEV37	Incorrect treatment group IP dispensed to subject	Yes	case by case basis	IP Compliance		If randomized treatment is different from actual treatment
PDEV38	Non-compliant with IP usage	Yes	case by case basis	IP Compliance		Check if <80% of >120%
PDEV39	IP not taken in compliance with protocol eg, at the appropriate times, during/timed with meals/snacks	case by case basis	case by case basis	IP Compliance		From monitoring log/Medical Review
PDEV40	Subject did not sign ICF and was enrolled	Yes	Yes	Informed Consent Criteria		ICF date is greater than randomization date

Protocol Deviation number	Protocol Deviation	Important	Clinically Important	Type criteria	Inclusion/Exclusion criteria number	Check
PDEV41	Subject used prohibited medication(s)	case by case basis	case by case basis	Other Criteria		Medical review
PDEV42	Lab safety and/or PK samples not drawn according to protocol requirements	case by case basis	case by case basis	Laboratory Assessment Criteria		Monitoring deviation log, Medical review

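### The SAP compliance formula credits 36 capsules per week instead of the capsules dispensed, so fully adherent early stoppers can be flagged below 80% or above 120%, depending on how X is read

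*SAP*

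**What the plan says.** SAP Section 15 (Treatment Compliance and Exposure) describes compliance in words as capsules taken divided by capsules that should have been taken. The formula for "compliance for X weeks of treatment" then puts 36 × X minus returned capsules in the numerator. The denominator is 4 times the "number of days between first intake and last intake of" the period. The result is tabulated overall ("ie from first intake to last intake of 12-week treatment period").

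Under Exposure, the same section gives three facts that bear on the numerator:

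- One kit covers one week plus two days and holds 36 capsules.
- Supply is issued ahead: "On trial visit days, subjects will be given treatment kits containing the number of capsules needed up to next planned trial visit".
- For cumulative dose, "The number of ingested capsules will be computed as the difference between the dispensed amount of capsules and the returned amount of capsules".

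The extension-period and overall compliance reuse the formula, with tablets or capsules/tablets in place of capsules. Neither document gives the number of tablets in an extension kit.

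PDEV38 in SAP Appendix 3 (Section 19.3), non-compliance with the investigational product, has the programmed check "Check if <80% of >120", evidently meaning below 80% or above 120%. It is marked important in every case and clinically important case by case. It names no formula, and Section 15 holds the only compliance definition in the SAP.

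**The concern.** Section 15 counts capsules taken in two ways. The cumulative-dose rule starts from what was handed out; the compliance rule starts from 36 for each of X weeks. A subject who stops between dispensing visits returns capsules from kits that 36 × X may not include, so the subtraction removes capsules that were never credited. In the other direction, if X is fixed at 12, the subject is credited with kits never received.

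A subject who took every capsule up to the last dose could therefore be reported as poorly compliant or as over-dosed, and be entered as an important protocol deviation. Such stops are foreseeable. Safety laboratory samples are taken at the visits where kits are issued (Protocol Table 1), and Protocol Section 6.5.4 ties withdrawal of treatment to the results, so some stops may come just after new kits are handed out.

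**Working it through.** **Inputs.** 4 capsules per day for 84 days and 36 capsules per kit (SAP Section 15). Dispensing visits on Days 1, 8, 15, 29, 43 and 57, with treatment ending at Day 85 (Protocol Section 5.1 and Table 1).

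**Assumptions.** Visits fall on nominal days, each interval gets the fewest whole kits that cover it, all unused capsules are returned, and nothing is dispensed at the stopping visit.

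**The plan's own constant.** (7 + 2) days × 4 = 36 capsules per kit, as stated.

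**Kits per interval.** The intervals are 7, 7, 14, 14, 14 and 28 days. Needs of 28, 28, 56, 56, 56 and 112 capsules call for 1, 1, 2, 2, 2 and 4 kits: 12 kits, or 432 capsules.

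**Completer.** Taken 4 × 84 = 336; returned 432 − 336 = 96. With X = 12 the formula gives (36 × 12 − 96)/(4 × 84) = 336/336 = 100%. It is right here because 12 weeks happens to equal 12 kits.

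**Adherent early stopper.** With last dose on Day d and K kits dispensed, returned = 36K − 4d. Counting days inclusively,

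compliance = 100 × (36X − 36K + 4d)/(4d).

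This is 100% only when X = K. With X = d/7 it becomes 228.6% − 900% × K/d, which is below 80% when d is less than about 6.06 × K.

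| Last dose | Dispensed | Taken | Returned | X = d/7 | X rounded up | X = 12 | Dispensed − returned |
|---|---|---|---|---|---|---|---|
| Day 16 | 144 | 64 | 80 | 3.6% | 43.8% | 550% | 100% |
| Day 20 | 144 | 80 | 64 | 48.6% | 55.0% | 460% | 100% |
| Day 28 | 144 | 112 | 32 | 100% | 100% | 357.1% | 100% |
| Day 56 | 288 | 224 | 64 | 100% | 100% | 164.3% | 100% |
| Day 62 | 432 | 248 | 184 | 54.4% | 56.5% | 100% | 100% |
| Day 70 | 432 | 280 | 152 | 74.3% | 74.3% | 100% | 100% |
| Day 77 | 432 | 308 | 124 | 88.3% | 88.3% | 100% | 100% |

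Day 62 in full, with X = 9: (324 − 184)/248 = 56.5%. If the day count is exclusive (61 days), it is 140/244 = 57.4%. For Day 20 the exclusive count gives 38.86/76 = 51.1% (X = 20/7) and 44/76 = 57.9% (X = 3).

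**How often.** Over the 82 possible last-dose days from Day 2 to Day 83, inclusive count:

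- X = d/7: 50 days below 80%.
- X rounded up: 30 days below 80%.
- X rounded down: 63 days below 80%.
- X = 12: none below 80%; all 55 days from Day 2 to Day 56 above 120%.
- X = kits dispensed: none outside 80–120%.

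With the exclusive count the first three become 45, 28 and 62. These are counts of days, not probabilities for subjects.

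**Extension.** The effect depends on a kit size that the documents do not give. If a weekly kit held 28 tablets (an assumption), an adherent 26-week completer with nothing to return would score (36 × 26)/(4 × 182) = 936/728 = 128.6%. With 36 tablets per kit the subject would return 936 − 728 = 208 and score 728/728 = 100%.

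**The case against.** The best reply is that X is undefined rather than wrong. Since 36 is one kit and kits are sized by the week, X could be meant as the number of weekly kits supplied. The formula is then the same as dispensed minus returned, and every adherent stopper scores 100%. That would be a sound rule, but the SAP does not state it. The text says weeks of treatment, and the denominator runs over actual intake, which points to weeks treated.

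Other parts of the reply stand in full:

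- A reader might infer that adherent subjects who stop early generally fall below 80%. They do not. Stops near the end of a dispensing interval score about 80–100%, and with X = 12 the error runs upward.
- A reader might infer that the denominator is a day short, giving a completer 336/(4 × 83) = 101.2%. SAP Section 11 sets stop date minus start date plus 1 as the default for durations, which largely answers this, and 101.2% is harmless against a 120% limit. The wording is still worth tightening: on an exclusive count an adherent stop on Day 5 scores 20/16 = 125% even with dispensed minus returned.
- A reader might infer that the M2951 arm would look non-adherent. That needs unequal stopping between arms, which the documents do not predict. The sample-size dropout allowance is only 6.25% of 64, or 4 subjects.
- Important deviations are confirmed at or before a Data Review Meeting (SAP Section 10.1), and Section 15 requires a listing of kits with ingested and returned counts, so an odd percentage could be noticed.
- The extension kit size is a gap, not a demonstrated error; Protocol Section 6.6 leaves packaging detail to a separate manual.

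**Conclusion.** The point holds in this limited form. The compliance numerator conflicts with the SAP's own definition of ingested capsules and matches it only when X equals kits dispensed. Because X is undefined for early stoppers, one fully adherent subject with last dose on Day 20 can be reported at about 49–58%, at 100% or at 460%. A Day 62 stopper can be reported at about 54–57% or at 100%. Rounding X down would lower the first figure in each case, as would extra kits issued to cover visit windows.

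The consequence is modest. The compliance table and the PDEV38 entries in the important-deviation table and listing can be wrong, and a false flag could enter a case-by-case decision on exclusion from an analysis set. No per-protocol analysis is planned (SAP Section 10.1), and the primary ACR20 analysis uses the mITT set without reference to compliance, so the documents give no ground for concern about the primary result. The percentages rest on the dispensing assumptions listed with the calculation; the conflict between the two definitions does not.

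**What to change.** In SAP Section 15, replace the formula, for each of the three periods, with:

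100 × (units dispensed − units returned) / (4 × (last dose date − first dose date + 1)).

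Units are the capsules or tablets recorded as dispensed in the accountability data, so no kit-size constant is needed for the extension. Writing the +1 explicitly aligns the denominator with the duration convention in Section 11. In PDEV38, correct "of" to "or" and refer to this formula.

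With this rule a fully adherent subject scores 100% whatever the last-dose day. The cost is a few lines of SAP text and the matching programming. No new data are needed, because the cumulative-dose calculation already uses dispensed and returned amounts.
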